## 6.5 Ipilimumab Dose Discontinuation

Ipilimumab should be permanently discontinued if any of the following criteria are met:

- Any Grade ≥ 2 drug-related uveitis or eye pain or blurred vision that does not respond to topical therapy and does not improve to Grade 1 severity within 2 weeks OR requires systemic treatment;

- Any Grade  $\geq$  3 bronchospasm or other hypersensitivity reaction;
- Any other Grade 3 non-skin, drug-related adverse event with the following exceptions for laboratory abnormalities, grade 3 nausea and vomiting, grade 3 neutropenia and thrombocytopenia, and symptomatic endocrinopathies which resolved (with or without hormone substitution);
- Any drug-related liver function test (LFT) abnormality that meets the following criteria require discontinuation:
  - AST or ALT  $>$  8x ULN
  - Total bilirubin  $>$  5 x ULN
  - Concurrent AST or ALT  $>$  3 x ULN and total bilirubin  $>$  2 x ULN
- Any Grade 4 drug-related adverse event or laboratory abnormality, except for the following events, which do not require discontinuation:
  - Grade 4 neutropenia  $\square$  7 days
  - Grade 4 lymphopenia or leukopenia
  - Isolated Grade 4 amylase or lipase abnormalities which are not associated with symptoms or clinical manifestations of pancreatitis. The PI should be consulted for Grade 4 amylase or lipase abnormalities.
  - Isolated Grade 4 electrolyte imbalances/abnormalities that are not associated with clinical sequelae and are corrected with supplementation/appropriate management within 72 hours of their onset
- Any treatment delay resulting in no ipilimumab dosing for  $>$  12 weeks with the following exceptions: Dosing delays to manage drug-related adverse events, such as prolonged steroid tapers, are allowed. Prior to re-initiating treatment in a subject with a dosing delay lasting  $>$  12 weeks, the PI must be consulted. Tumor assessments should continue as per protocol even if dosing is delayed.
- Dosing delays resulting in no ipilimumab dosing for  $>$  12 weeks that occur for non-drug related reasons may be allowed if approved by the PI. Prior to reinitiating treatment in a subject with a dosing delay lasting  $>$  12 weeks, the PI must be consulted. Tumor assessments should continue as per protocol even if dosing is delayed.
- Any adverse event, laboratory abnormality, or intercurrent illness which, in the judgment of the Investigator, presents a substantial clinical risk to the subject with continued ipilimumab dosing

The assessment for discontinuation of ipilimumab should be made separately from the assessment made for discontinuation of nivolumab. Although there is overlap among the discontinuation criteria, if discontinuation criteria are met for ipilimumab but not for nivolumab, treatment with nivolumab may continue if ipilimumab is discontinued.

If a subject meets criteria for discontinuation and investigator is unable to determine whether the event is related to both or one study drug, the subject should discontinue both nivolumab and ipilimumab and be taken off the treatment phase of the study.

## 6.6 Criteria to Resume Nivolumab Dosing

Subjects may resume treatment with nivolumab when the drug-related AE(s) resolve(s) to

Grade  $\leq$  1 or baseline, with the following exceptions:

---

CONFIDENTIAL

*This document is confidential. Do not disclose or use except as authorized.*

IRB APPROVED

- Subjects may resume treatment in the presence of Grade 2 fatigue.
- Subjects who have not experienced a Grade 3 drug-related skin AE may resume treatment in the presence of Grade 2 skin toxicity.
- Subjects with combined Grade 2 AST/ALT and total bilirubin values meeting discontinuation parameters (Section 6.7) should have treatment permanently discontinued.
- Drug-related pulmonary toxicity, diarrhea, or colitis must have resolved to baseline before treatment is resumed. Subjects with persistent Grade 1 pneumonitis after completion of a steroid taper over at least 1 month may be eligible for retreatment if discussed with and approved by the PI.
- Subjects who received systemic corticosteroids for management of any drug-related toxicity must be off corticosteroids or have tapered down to an equivalent dose of prednisone  $\geq$  10 mg/day.
- Drug-related endocrinopathies adequately controlled with only physiologic hormone replacement may resume treatment.
- Subjects who delay study treatment due to any Grade  $\geq$  3 amylase or lipase abnormality that is not associated with symptoms or clinical manifestations of pancreatitis, and that is assessed by the investigator to be related to ipilimumab and not to nivolumab, may resume nivolumab when the amylase or lipase abnormality has resolved to Grade  $<$  3. The PI should be consulted prior to resuming nivolumab in such subjects.
- Dose delay of nivolumab which results in treatment interruption of  $>$  6 weeks requires treatment discontinuation, with exceptions as noted in Section 6.7.

## 6.7 Criteria to Resume Ipilimumab Dosing

Subjects may resume treatment with nivolumab and ipilimumab when drug-related AE(s) resolve(s) to Grade 1 or baseline value, with the following exceptions:

- Subjects may resume treatment in the presence of Grade 2 fatigue.
- Subjects who have not experienced a Grade 3 drug-related skin AE may resume treatment in the presence of Grade 2 skin toxicity.
- Subjects with baseline Grade 1 AST/ALT or total bilirubin who require dose delays for reasons other than a 2-grade shift in AST/ALT or total bilirubin may resume treatment in the presence of Grade 2 AST/ALT or total bilirubin.
- Subjects with combined Grade 2 AST/ALT and total bilirubin values meeting discontinuation parameters (given below) should have treatment permanently discontinued.
- Drug-related pulmonary toxicity, diarrhea, or colitis must have resolved to baseline before treatment is resumed.
- Subjects who received systemic corticosteroids for management of any drug-related toxicity must be off corticosteroids or have tapered down to an equivalent dose of prednisone  $\leq$  10 mg/day.
- Drug-related endocrinopathies adequately controlled with only physiologic hormone replacement may resume treatment after consultation with the PI.
- Dose delay of ipilimumab which results in no ipilimumab dosing for  $>$  12 weeks requires ipilimumab discontinuation, with exceptions as noted below.
- Ipilimumab may not be resumed sooner than 6 weeks ( $\pm$  5days) after the prior ipilimumab dose.

- In general, subjects who meet criteria to resume ipilimumab will also have met criteria to resume nivolumab, so it should be feasible to synchronize dosing of both drugs when resuming ipilimumab. In order to facilitate this, the dosing days of nivolumab and ipilimumab may be adjusted within the permitted  $\pm$  5 day window, as long as consecutive nivolumab doses are given at least 12 days apart.
- One exception to note is when ipilimumab and nivolumab doses are delayed due to drug related Grade  $\geq$  3 amylase or lipase abnormalities not associated with symptoms or clinical manifestations of pancreatitis. If the investigator assesses the Grade  $\geq$  3 amylase or lipase abnormality to be related to ipilimumab and not related to nivolumab, nivolumab may be resumed when the amylase or lipase abnormality resolves to Grade  $<$  3 but ipilimumab may only be resumed when the amylase or lipase abnormality resolves to Grade 1 or baseline. Investigator attribution of this toxicity to the ipilimumab dosing must be clearly noted in the subject's medical chart. The PI should be consulted prior to resuming nivolumab in such subjects.

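### Sections 6.6 and 6.7 contradict each other on restarting nivolumab when liver tests are at Grade 2

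*Combined protocol and SAP*

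**What the plan says.** Section 6.2 requires that, for patients on the combination, a toxicity that meets the delay criteria holds both drugs until the retreatment criteria are met. Those criteria are in two places.

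- **Section 6.6 (nivolumab):** "Subjects may resume treatment with nivolumab when the drug-related AE(s) resolve(s) to" Grade 1 or lower, or baseline, subject to a list of exceptions. The list includes Grade 2 fatigue, Grade 2 skin toxicity and, with PI approval, lung toxicity: "Subjects with persistent Grade 1 pneumonitis after completion of a steroid taper over at least 1 month may be eligible for retreatment". Its only liver bullet concerns permanent stopping: combined values "meeting discontinuation parameters (Section 6.7) should have treatment permanently discontinued".
- **Section 6.7 (headed ipilimumab):** "Subjects may resume treatment with nivolumab and ipilimumab when drug-related AE(s) resolve(s) to Grade 1 or baseline value", again with exceptions. One is for liver tests: "Subjects with baseline Grade 1 AST/ALT or total bilirubin who require dose delays for reasons other than a 2-grade shift" in those values "may resume treatment in the presence of Grade 2 AST/ALT or total bilirubin". Pulmonary toxicity must be back to baseline, with no Grade 1 pneumonitis exception.

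Section 6.7 also describes how the two sets relate: in general, "subjects who meet criteria to resume ipilimumab will also have met criteria to resume nivolumab". The only departure it names concerns amylase and lipase.

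**The concern.** Because both drugs are held together and the opening sentence of 6.7 names nivolumab, both sections apply to the same patient at the same restart decision. If they disagree, a site can follow the protocol and still reach either answer.

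Section 6.1 permits no dose reductions, so delay, restart and discontinuation are the main dosing controls for toxicity. Section 7.5 lists hepatitis and pneumonitis among the most common types of immune-mediated event, and the trial has several centres. Different readings would make dosing inconsistent between sites, with consequences for patient safety, for exposure to the combination, and for the discontinuations counted under the tolerability objective.

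**Working it through.** No arithmetic applies to the contradiction itself. The check applies both sections, read with 6.2, to the same hypothetical patients.

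| Patient at the restart decision | Section 6.6 | Section 6.7 |
|---|---|---|
| A. Baseline Grade 1 AST; dosing held for another event, now resolved; AST now Grade 2 and judged drug-related; combined-value stopping rule not met | Nivolumab may not restart: Grade 2 is above Grade 1 and above baseline, and no exception applies | Nivolumab and ipilimumab may restart under the liver exception |
| B. No lung disease at baseline; drug-related pneumonitis persisting at Grade 1 after a steroid taper of at least 1 month; PI approves | Nivolumab may restart | Restart not allowed: baseline not reached |

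**Patient A.** The combination is permitted where nivolumab is not. A stricter rule for ipilimumab cannot explain this, because here the ipilimumab section is the more permissive one. The patient also meets the 6.7 criteria without meeting those of 6.6, which is the reverse of the relation 6.7 describes, and liver tests are not its named departure.

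Section 6.2 adds a further mismatch. Its specific rule for patients with baseline Grade 1 liver tests calls for delay only at drug-related Grade 3 or higher. A Grade 2 value that would not trigger a delay under that rule would still block a nivolumab restart under 6.6.

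**Does 6.6 look only at the event that caused the delay?** If so, the Grade 2 AST would be ignored and the conflict would vanish. The list in 6.6 suggests otherwise. It makes exceptions for Grade 2 fatigue and Grade 2 skin toxicity, although 6.2 exempts fatigue from its Grade 2 delay rule and delays for skin events from Grade 3. Section 6.7 carries the same two exceptions and still has a separate one for Grade 2 liver values.

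**Could 6.7 govern every joint restart and 6.6 only nivolumab given alone?** The text does not say this. It would also make the answer depend on the visit: nivolumab is given every 2 weeks and ipilimumab every 6, so the same liver value would permit treatment at a joint visit and bar it at a nivolumab-only visit.

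**Patient B.** Here 6.7 is the stricter section. That fits a deliberate tighter condition for ipilimumab or for the combination. The doubt arises only because the opening sentence of 6.7 names nivolumab.

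**Stopping parameters.** Section 6.6 refers to 6.7 for the combined liver values, and 6.7 says they follow below but gives none. They stand in 6.4 and in 6.5, and are identical: AST or ALT above 3 x ULN together with total bilirubin above 2 x ULN.

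**The case against.** The best case on the other side is that the liver conflict is narrow and depends on interpretation. The Grade 2 value must be drug-related, and 6.6 must be read as covering every drug-related event present. The argument from the fatigue and skin exceptions is not conclusive, since 6.2 also lets the investigator delay for any event in his or her judgment, so those events could themselves have caused a delay. The statement relating the two sets of criteria is qualified as general. Appendix B holds the hepatic and pulmonary management algorithms, and its content is not in the text available for review. All of this stands as a limit. It does not remove the contradiction: on its ordinary reading 6.6 bars what 6.7 allows, and the restart bullets do not defer to Appendix B.

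Three stronger inferences are tempting and are not supported.

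- **That the pneumonitis difference is a second outright contradiction.** The protocol assesses discontinuation separately for each drug, lets nivolumab continue after ipilimumab stops, and in the amylase/lipase case lets nivolumab restart before ipilimumab. A stricter condition in 6.7 is coherent with that, and the 6.6 exception needs PI approval. What remains is an ambiguity of scope.
- **That the misdirected reference would change decisions.** The parameters in 6.4 and 6.5 agree, so it is editorial.
- **That several of the 54 patients would be affected**, judging from the Grade 3/4 hepatic rates in Section 2.2 (10% in lung arm B, 15% in the melanoma concurrent regimens). Those rates count the wrong events. From baseline Grade 1, a rise to Grade 3 is a shift of 3 - 1 = 2 grades, and a delay for that shift falls outside the 6.7 exception. The regimens differ too. Arm B used nivolumab 1 mg/kg, whereas the regimen here matches arm D, where hepatic Grade 3/4 events were below 10%. Of the 53 melanoma patients, 14 + 17 + 6 = 37 received ipilimumab 3 mg/kg.

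**Conclusion.** The contradiction on Grade 2 liver tests is in the text and should be reconciled. It applies to patients with baseline Grade 1 AST/ALT or bilirubin, held for a reason other than a 2-grade liver shift, whose values are Grade 2 at restart and do not meet the combined stopping rule. It assumes that the Grade 2 value is drug-related and that 6.6 covers all drug-related events present. The pneumonitis difference is a secondary question of scope, and the pointer is an editorial error.

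The documents give no frequency for baseline Grade 1 liver values, for the liver pattern described, or for residual Grade 1 pneumonitis. The number of patients affected therefore cannot be derived and may be small. The issue bears on safety and on consistent dosing across sites. The sample size and the primary analysis are unaffected, and any influence on response through exposure is indirect and not quantifiable from the documents.

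**What to change.** The sponsor should:

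1. Reconcile 6.6 and 6.7 on restarting with Grade 2 AST/ALT or bilirubin, and check the result against the 6.2 delay rule for baseline Grade 1 values.
2. State for the liver condition and the pneumonitis condition whether each applies to nivolumab alone, to ipilimumab, or to both, and align the opening sentence of 6.7 with that statement.
3. Point the combined liver-value stopping rule in both sections to 6.4 and 6.5.

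Which clinical condition is intended is for the sponsor to settle; this review does not propose one. The cost is wording in Section 6 and a memo to sites, with no added visits or tests.

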### **Treatment of Nivolumab or Ipilimumab Related Infusion Reactions**

Since nivolumab and ipilimumab contain only human immunoglobulin protein sequences, it is unlikely to be immunogenic and induce infusion or hypersensitivity reactions. However, if such a reaction were to occur, it might manifest with fever, chills, rigors, headache, rash, pruritis, arthralgias, hypo- or hypertension, bronchospasm, or other symptoms. All Grade 3 or 4 infusion reactions should be reported as an SAE if criteria are met. Infusion reactions should be graded according to NCI CTCAE (version 4.0) guidelines. Treatment recommendations are provided below and may be modified based on local treatment standards and guidelines as appropriate:

**For Grade 1 symptoms:** (Mild reaction; infusion interruption not indicated; intervention not indicated)

Remain at bedside and monitor subject until recovery from symptoms. The following prophylactic premedications are recommended for future infusions: diphenhydramine 50 mg (or equivalent) and/or paracetamol 325 to 1000 mg (acetaminophen) at least 30 minutes before additional nivolumab administrations.

**For Grade 2 symptoms:** (Moderate reaction requires therapy or infusion interruption but responds promptly to symptomatic treatment [eg, antihistamines, non-steroidal anti-inflammatory drugs, narcotics, corticosteroids, bronchodilators, IV fluids]; prophylactic medications indicated for 24 hours).

Stop the nivolumab or ipilimumab infusion, begin an IV infusion of normal saline, and treat the subject with diphenhydramine 50 mg IV (or equivalent) and/or paracetamol 325 to 1000 mg (acetaminophen); remain at bedside and monitor subject until resolution of symptoms. Corticosteroid or bronchodilator therapy may also be administered as appropriate. If the infusion is interrupted, then restart the infusion at 50% of the original infusion rate when symptoms resolve; if no further complications ensue after 30 minutes, the rate may be increased to 100% of the original infusion rate. Monitor subject closely. If symptoms recur, then no further nivolumab or ipilimumab will be administered at that visit. Administer diphenhydramine 50 mg IV, and remain at bedside and monitor the subject until resolution of symptoms. The amount of study drug infused must be recorded on the electronic case report form (eCRF). The following

prophylactic premedications are recommended for future infusions: diphenhydramine 50 mg (or equivalent) and/or paracetamol 325 to 1000 mg (acetaminophen) should be administered at least 30 minutes before additional nivolumab or ipilimumab administrations. If necessary, corticosteroids (recommended dose: up to 25 mg of IV hydrocortisone or equivalent) may be used.

**For Grade 3 or Grade 4 symptoms:** (Severe reaction, Grade 3: prolonged [ie, not rapidly responsive to symptomatic medication and/or brief interruption of infusion]; recurrence of symptoms following initial improvement; hospitalization indicated for other clinical sequelae [eg, renal impairment, pulmonary infiltrates]). Grade 4: (life threatening; pressor or ventilatory support indicated).

Immediately discontinue infusion of nivolumab or ipilimumab. Begin an IV infusion of normal saline, and treat the subject as follows. Recommend bronchodilators, epinephrine 0.2 to 1 mg of a 1: 1,000 solution for subcutaneous administration or 0.1 to 0.25 mg of a 1: 10,000 solution injected slowly for IV administration, and/or diphenhydramine 50 mg IV with methylprednisolone 100 mg IV (or equivalent), as needed. Subject should be monitored until the investigator is comfortable that the symptoms will not recur. Nivolumab or ipilimumab will be permanently discontinued. Investigators should follow their institutional guidelines for the treatment of anaphylaxis. Remain at bedside and monitor subject until recovery from symptoms. In the case of late-occurring hypersensitivity symptoms (eg, appearance of a localized or generalized pruritis within 1 week after treatment), symptomatic treatment may be given (eg, oral antihistamine, or corticosteroids).

#### **6.7.1 Management Algorithms for Immuno-Oncology Agents**

Immuno-oncology (I-O) agents are associated with adverse events that can differ in severity and duration than adverse events caused by other therapeutic classes. Nivolumab and ipilimumab are considered immuno-oncology agents in this protocol. Management algorithms have been developed to assist investigators in assessing and managing the following groups of adverse events: Gastrointestinal, Renal, Pulmonary, Hepatic, Endocrinopathies, Skin, and Neurological.

Early recognition and intervention are recommended according to the management algorithms; and in addition include ophthalmologic evaluations for any visual symptoms in order to evaluate for nivolumab or ipilimumab related uveitis.

The recommendations are to follow the algorithms in the nivolumab investigator brochure for immune related events; while the ipilimumab investigator brochure contains similar algorithms, the algorithms in the nivolumab brochure have been aligned to accommodate combinations as well as nivolumab monotherapy.

Therefore, the algorithms recommended for utilization are in Appendix B for reference.

Additional details on the safety of nivolumab and ipilimumab, including results from clinical studies, are available in the IB.

---

CONFIDENTIAL

*This document is confidential. Do not disclose or use except as authorized.*

IRB APPROVED

## 6.8 Concomitant Treatments

### 6.8.1 Prohibited and/or Restricted Treatments

The following medications are prohibited during the study (unless utilized to treat a drug related adverse event):

- Immunosuppressive agents.
- Immunosuppressive doses of systemic corticosteroids (except as stated in section 6.8.2)
- Any concurrent anti-neoplastic therapy (i.e., chemotherapy, hormonal therapy, immunotherapy, extensive, non-palliative radiation therapy, or standard or investigational agents for treatment of cancer)
- Surgical resection of tumor

Caution should be used regarding the use of herbal medications as there may be as yet unknown interactions with nivolumab and/or ipilimumab. Discontinuation of the use of herbal medications prior to study enrollment is encouraged. Except for the permitted procedures specified as palliative local therapies (Section 6.8.3), all other radiation therapy or surgery to any tumor lesion is not permitted during study treatment. Subjects who require such non-palliative procedures must be discontinued from study treatment.

### 6.8.2 Other Restrictions and Precautions

Subjects with a condition requiring systemic treatment with either corticosteroids ( $> 10$  mg daily prednisone equivalent) or other immunosuppressive medications within 14 days of first treatment are excluded. Inhaled or topical steroids, and adrenal replacement steroid doses  $> 10$  mg daily prednisone equivalent, are permitted in the absence of active autoimmune disease.

It is the local imaging facility 's responsibility to determine, based on subject attributes (eg, allergy history, diabetic history and renal status), the appropriate imaging modality and contrast regimen for each subject. Imaging contraindications and contrast risks should be considered in this assessment. Subjects with renal insufficiency should be assessed as to whether or not they should receive contrast and if so, what type and dose of contrast is appropriate. If CT is contraindicated for a subject because of an iodinated contrast allergy, then a contrast enhanced MRI of the neck, chest, abdomen and pelvis will be performed. Specific to MRI, subjects with severe renal insufficiency (ie, estimated glomerular filtration rate (eGFR)  $< 30$  mL/min/1.73m^2) are at increased risk of nephrogenic systemic fibrosis. MRI contrast should not be given to this subject population. In addition, subjects are excluded from MRI if they have tattoos, metallic implants, pacemakers, etc. The ultimate decision to perform MRI in an individual subject in this study rests with the site radiologist, the investigator and the standard set by the local Ethics Committee.

